4. INVESTIGATIONAL PLAN

4.1. Overall Study Design and Plan

This is a Phase 1, open label, dose-escalation clinical trial to evaluate the safety, reactogenicity, and immunogenicity of Sm-p80 + GLA-SE candidate schistosomiasis vaccine (SchistoShield®) in healthy adults 18 through 55 years of age. The Sm-p80 antigen is a recombinant protein produced in *E. coli* and GLA-SE is an immunological adjuvant.

Five treatment groups, each including nine subjects, will receive three intramuscular (IM) injections of 0.5 mL of designated study product on either Days 1, 29, and 57 or on Days 1, 29, and 180. Group A (unadjuvanted comparator) will receive 100 µg Sm-p80 alone on Days 1, 29, and 57; Group B (low dose standard schedule) will receive 10 µg Sm-p80 + 5 µg GLA-SE on Days 1, 29, and 57; Group C (mid dose delayed booster) will receive 30 µg Sm-p80 + 5 µg GLA-SE on Days 1, 29, and 180; Group D (mid dose standard schedule) will receive 30 µg Sm-p80 + 5 µg GLA-SE on Days 1, 29, and 57; Group E (high dose standard schedule) will receive 100 µg Sm-p80 + 5 µg GLA-SE on Days 1, 29, and 57. Dose escalation will proceed as described in the Protocol Summary (protocol v2.0).

Reactogenicity will be measured by the occurrence of solicited injection site and systemic reactions from the time of each study product injection through seven days after each study product injection. Unsolicited AEs of all severities, and concomitant medications, will be collected from the time of each study product injection through the next 28 days. During period of follow-up outside of the 28-day post-vaccination interval, only SAEs, medically attended adverse events (MAAEs), new onset chronic medical conditions (NOCMCs), and potentially immune-mediated medical conditions (PIMMCs) will be collected. Clinical laboratory evaluations for safety will be performed on venous blood collected prior to, and approximately seven days after, each study vaccination.

Immunogenicity testing will include measuring titers of total IgG against the Sm-p80 protein by ELISA. Gene expression will be evaluated using RNA Seq analysis from whole blood.

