11. IMMUNOGENICITY

11.1. Secondary Immunogenicity Analysis

11.1.1. ELISA (anti Sm-p80 Total IgG)

Antibody responses, measured by total IgG production to the recombinant Sm-p80 protein using ELISA will be presented at baseline (Day 1) and by study day (Days 8, 29, 36, 57 for all treatment groups; additionally Days 64, 85, 181 for Groups A, B, D, and E, and Days 180, 187, 208, 304 for Group C) using descriptive statistics in [Table 15](#) (mITT immunogenicity population). For post-baseline timepoints, geometric mean fold rise (GMFR) and the proportion of subjects with at least a 4-fold rise will be presented with 95% confidence intervals for mITT population in [Table 16](#) (mITT immunogenicity population). The ELISA seroresponse (at least 4-fold rise) rates at 28-days post vaccination will be compared between Group A vaccine group and each treatment group using Fisher's Exact Test ([Table 17](#)). Confidence intervals for proportions are calculated using Wilson Score methodology without continuity correction. Confidence intervals calculated for GMT and GMFR follow a t-distribution.

Antibody responses will be adjusted for baseline. Reverse cumulative distributions (RCD) curves will be presented with separate panels for each timepoint for mITT population in [Figure 2](#). Graphs of Geometric Mean Anti-Sm-p80 ELISA responses over time will be presented in [Figure 3](#). Individual time trends for each Anti-Sm-p80 ELISA will be presented in [Figure 4](#).

Results of individual total IgG immunogenicity responses, scheduled and unscheduled, will be presented in [Listing 9](#).

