	GMFR ^a (95% CI)	x.x (x.x, x.x)	x.x (x.x, x.x)	N/A	x.x (x.x, x.x)	x.x (x.x, x.x)
	Number (%) of Responders ^b	x (xx)	x (xx)	N/A	x (xx)	x (xx)
	95% CI	x.x, x.x	x.x, x.x	N/A	x.x, x.x	x.x, x.x
Study Day 180 (Group C: Pre-Dose 3)	n	N/A	N/A	x	N/A	N/A
	GMFR ^a (95% CI)	N/A	N/A	x.x (x.x, x.x)	N/A	N/A
	Number (%) of Responders ^b	N/A	N/A	x (xx)	N/A	N/A
	95% CI	N/A	N/A	x.x, x.x	N/A	N/A
Study Day 187 (Group C: 7 Days Post Dose 3)	n	N/A	N/A	x	N/A	N/A
	GMFR ^a (95% CI)	N/A	N/A	x.x (x.x, x.x)	N/A	N/A
	Number (%) of Responders ^b	N/A	N/A	x (xx)	N/A	N/A
	95% CI	N/A	N/A	x.x, x.x	N/A	N/A
Study Day 181 (Groups A, B, D, E: 124 Days Post Dose 3)	n	x	x	N/A	x	x

Table 16: Anti-Sm-p80 ELISA Total IgG Geometric Mean Fold Rise (GMFR) and Seroconversion Results by Time Point and Treatment Group, mITT Immunogenicity Population (Continued)

Time Point	Statistic	Group A: 100 µg Sm-p80 (unadjuvanted) (N=X)	Group B: 10 µg Sm-p80 + 5 µg GLA-SE (N=X)	Group C: 30 µg Sm-p80 + 5 µg GLA-SE (delayed booster) (N=X)	Group D: 30 µg Sm-p80 + 5 µg GLA-SE (N=X)	Group E: 100 µg Sm-p80 + 5 µg GLA-SE (N=X)
	GMFR ^a (95% CI)	x.x (x.x, x.x)	x.x (x.x, x.x)	N/A	x.x (x.x, x.x)	x.x (x.x, x.x)
	Number (%) of Responders ^b	x (xx)	x (xx)	N/A	x (xx)	x (xx)
	95% CI	x.x, x.x	x.x, x.x	N/A	x.x, x.x	x.x, x.x
Study Day 208 (Group C: 28 Days Post Dose 3)	n	N/A	N/A	x	N/A	N/A
	GMFR ^a (95% CI)	N/A	N/A	x.x (x.x, x.x)	N/A	N/A
	Number (%) of Responders ^b	N/A	N/A	x (xx)	N/A	N/A
	95% CI	N/A	N/A	x.x, x.x	N/A	N/A
Study Day 304 (Group C: 124 Days Post Dose 3)	n	N/A	N/A	x	N/A	N/A
	GMFR ^a (95% CI)	N/A	N/A	x.x (x.x, x.x)	N/A	N/A
	Number (%) of Responders ^b	N/A	N/A	x (xx)	N/A	N/A
	95% CI	N/A	N/A	x.x, x.x	N/A	N/A

Note: N = Number of subjects in the mITT Immunogenicity Population; n = Number of subjects with results at the given timepoint.

^a GMFR represents the geometric mean fold rise in antibody compared to pre-dose 1.^b Number of responders represents the percentage of subjects with at least a 4-Fold Rise in antibody compared to Day 1, pre-dose 1.

Pseudo Code:

```
/*Geometric Mean Fold Rise*/
data dsn2;
  set dsn1;
  log_fold = log(mchg);
proc means data= dsn2 n mean clm noint;
  by stdy trta;
  var log_fold;
  output out= gmfr0(drop= _type_ _freq_)
    n= n2
    mean= mean
    lclm= lclm
    uclm= uclm;
data gmfr;
  set gmfr0;
  gmfr = put(exp(mean),8.1);                                     /*geometric mean fold rise*/
  gmfr_l = put(exp(lclm), 8.1);                                  /*lower bound*/

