  gmfr_u = put(exp(uclm), 8.1);                                  /*upper bound*/
  gmfr_ci = strip(gmfr)||' ('||strip(gmfr_l)||', '||strip(gmfr_u)||')'; /*GMFR(95%CI)*/
run;

/*Seroresponders*/
proc freq data= dsn1 noint;
  table stdy*trta / out= totcnt(keep= stdy trta count rename= count=totcnt);

proc freq data= dsn1 noint;
  where crit1fl ^= ''; /*seroconversion flag = Y*/
  table stdy*trta / out= cnt(keep= stdy trta count);
```

Pseudo Code (*continued*):

```
data cntp;
merge cnt totcnt;
by stdy trta;
  if count=. then count=0;
  scn = put(count/totcnt*100, 5.1);
data cntci;
set cntp;
  sym = 1;           /*seroconversion*/
output;
  sym = 0;           /*no seroconversion*/
  count = totcnt - count;
output;
proc freq data= cntci;
by stdy trta;
tables sym / nocum norow binomial(cl= wilson);
weight count;           /*zeros: for CI of zero*/
  *exact binomial;
ods output binomial= binany (keep=stdy trta name1 nvalue1 where=(name1 in ('XL_BIN','XU_BIN')));
run;
```

Table 17: Comparison of Anti-Sm-p80 ELISA Total IgG Seroresponse Rates between Group A and Each Treatment Group 28-Days Post Dose – mITT Immunogenicity Population

Analysis Population	Dose	Statistic	Group A: 100 µg Sm-p80 (unadjuvanted) (N=X)	Group B: 10 µg Sm-p80 + 5 µg GLA-SE (N=X)	Group C: 30 µg Sm-p80 + 5 µg GLA-SE (delayed booster) (N=X)	Group D: 30 µg Sm-p80 + 5 µg GLA-SE (N=X)	Group E: 100 µg Sm-p80 + 5 µg GLA-SE (N=X)
mITT Immunogenicity Population	1	Fraction Responders, n ^a	x	x	x	x	x
		Responders, Rate	xx%	xx%	xx%	xx%	xx%
		95% CI ^b	x.XXX, x.XXX	x.XXX, x.XXX	x.XXX, x.XXX	x.XXX, x.XXX	x.XXX, x.XXX
		Difference in Proportion	--	x.XXX	x.XXX	x.XX	x.XXX
		p-value ^c	--	0.XXXX	0.XXXX	0.XXXX	0.XXXX
	2	...					
	3	...					
Per Protocol Population					

^a Responder is defined as subjects with at least a 4-fold rise in antibody compared to pre-dose 1.^b 95% confidence intervals are from the Wilson score method without continuity correction.^c P-values were calculated using Fisher's Exact Test.

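### As written, the Table 16 pseudo code cannot return the Wilson interval for responders that SAP Section 11.1.1 promises

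*SAP*

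**What the plan says.** SAP Section 11.1.1 states that "the proportion of subjects with at least a 4-fold rise will be presented with 95% confidence intervals", and that "Confidence intervals for proportions are calculated using Wilson Score methodology without continuity correction". Footnote b of Table 16 (SAP Appendix 1, section 14.2) fixes which subjects the row describes: "Number of responders represents the percentage of subjects with at least a 4-Fold Rise in antibody compared to Day 1, pre-dose 1".

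The seroresponder pseudo code under Table 16 works in this order:

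- It counts responders with the filter "where crit1fl ^= ''; /*seroconversion flag = Y".
- It forms the printed percentage from responders over total: "scn = put(count/totcnt*100, 5.1".
- It writes two records per group and time point: `sym` = 1 for seroconversion and `sym` = 0 for none.
- It runs the frequency procedure on `sym` with "tables sym / nocum norow binomial(cl= wilson". No level or order option is shown.
- It weights by the count. The words about zeros appear only in a comment beside that statement.
- It has the exact request commented out.
- It keeps for printing only the rows where "name1 in ('XL_BIN','XU_BIN".

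**The concern.** The step contradicts itself and the SAP text. It requests Wilson limits and disables the exact request, yet keeps only limits with exact-limit names. It also never says that the proportion of interest is the one for `sym` = 1. If the procedure takes the first sorted level, the limits describe subjects who did not seroconvert, while the percentage printed beside them describes those who did.

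Seroconversion about 28 days after each vaccination is a secondary endpoint (SAP Section 3.2.2), and Protocol Section 10.5.3 promises its 95% CI by time point and group. Table 16 belongs to both interim analyses (SAP Section 6.2), which run on cleaned but unlocked data. SAP Section 6.6.2 allows those reports to be made public and used in the developers' decisions. A wrong interval would be obvious at extreme response rates but would look plausible near 50%.

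**Working it through.** **Inputs.** Group size is 9 ("Five treatment groups, each including nine subjects", SAP Section 4.1), if no result is missing. The confidence level is 95%, so z = 1.960 and z² = 3.8415. The Table 16 cells are placeholders, so the plan prints no interval to reproduce. As a check on the group size, 1 − 0.8⁹ = 0.866, which matches SAP Table 4 for an event probability of 0.20.

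**Assumptions about SAS (not in the documents, not run).** (1) With no level stated, the binomial analysis uses the first level in sorted order, here `sym` = 0. (2) `XL_BIN` and `XU_BIN` are the exact (Clopper-Pearson) limits. (3) Without a zeros option on the weight statement, a level with zero count drops out.

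**What the step can return.** If the output table holds no `XL_BIN`/`XU_BIN` rows, because Wilson was requested and exact was commented out, the CI cell is empty. If it does hold them, they are exact limits for the first level. In neither case are they Wilson limits for responders.

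**Formulas.** For k responders of n:

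- Wilson: [p + z²/(2n) ± z·√(p(1−p)/n + z²/(4n²))] / (1 + z²/n), with p = k/n.
- Exact, for m events of n: lower = 0.025 quantile of Beta(m, n−m+1), upper = 0.975 quantile of Beta(m+1, n−m). For non-responders, m = n−k.

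**Worked case, 7/9.** Here p = 0.7778.

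- Divisor: 1 + 3.8415/9 = 1.4268.
- Centre: (0.7778 + 0.2134)/1.4268 = 0.6947.
- Half-width: 1.960 × √(0.01920 + 0.01186)/1.4268 = 0.2421.
- Wilson interval for responders: 45.3–93.7%.
- Exact interval for the 2/9 non-responders: 2.8–60.0%, which excludes 77.8%.

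**All outcomes at n = 9, when exact limits are present:**

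| Responders | Printed rate (%) | Wilson, as promised (%) | Limits from the code (%) | Contains printed rate? |
|---|---|---|---|---|
| 0 | 0.0 | 0.0–29.9 | 66.4–100 | no |
| 1 | 11.1 | 2.0–43.5 | 51.8–99.7 | no |
| 2 | 22.2 | 6.3–54.7 | 40.0–97.2 | no |
| 3 | 33.3 | 12.1–64.6 | 29.9–92.5 | yes |
| 4 | 44.4 | 18.9–73.3 | 21.2–86.3 | yes |
| 5 | 55.6 | 26.7–81.1 | 13.7–78.8 | yes |
| 6 | 66.7 | 35.4–87.9 | 7.5–70.1 | yes |
| 7 | 77.8 | 45.3–93.7 | 2.8–60.0 | no |
| 8 | 88.9 | 56.5–98.0 | 0.3–48.2 | no |
| 9 | 100 | 70.1–100 | 66.4–100 | yes |

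At 9/9 the empty `sym` = 0 level drops out, so the limits fall on responders, though they are still exact rather than Wilson.

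**Partial repairs are not enough.**

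- Right level, exact limits kept: 7/9 gives 40.0–97.2% instead of 45.3–93.7%.
- Wilson limits, level still unset: the interval misses the printed rate at 0–3 and 6–8 responders.
- Zeros kept, level still unset: 9/9 would give exact limits of 0.0–33.6% beside a printed 100%.

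**The case against.** The strongest objection is that the numerical harm rests on software behaviour the documents do not describe. That stands in part. It would be too much to say that the code returns 2.8–60.0% at 7/9; it may return nothing, and an empty cell would be noticed. What needs no run is the mismatch between requesting Wilson and keeping limits with other names, and the absence of any stated level.

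Second, the block was read from a PDF and has at least one apparent misreading (an option printed as `noint`, probably `noprint`). A level or zeros option could have been lost. That weakens those two parts. The line naming the kept limits is clear, and if the level had been set in the original, the result would still be exact rather than Wilson.

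Third, this is pseudo code. SAP Section 11.1.1 and the footnotes to Tables 16 and 17 state the right method and the right subjects, and SAP Section 14 allows R as well as SAS. A programmer who follows the text avoids the error. This limits its weight but is no reason to leave contradictory code in the plan.

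Three stronger readings are tempting but not supported:

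- A reader might infer that the missing zeros option causes the failure at 0/9. It does not. With no level set, `sym` = 0 holds all nine subjects and is analysed with or without that option.
- A reader might infer that the filter counts non-responders as responders. It keeps every non-missing flag, but the SAP does not define the flag's values. If the flag is Y or blank, the filter is correct.
- A reader might infer that Table 17 carries the same faulty code. It has no pseudo code, and its footnote already states Wilson.

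**Conclusion.** The point holds for the Table 16 pseudo code only: it is wrong as written, while the SAP text is right. The step does not produce Wilson limits for responders. On the assumed SAS defaults it gives either no limits or exact limits for non-responders. In the latter case, with nine results per group, the interval misses its own estimate at five of the ten possible outcomes (0, 1, 2, 7 and 8 responders) and contains it at the other five (3 to 6, and 9).

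The binomial step does not alter the printed percentage. The analyses are descriptive, and no decision rule in the documents uses this interval. The matter still deserves correction, because the interval accompanies a secondary endpoint in both interim reports and the final report. The documents do not show that the chosen method is unsound or that any reported result is wrong, and neither should be inferred.

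**What to change.** Change four lines of the Table 16 pseudo code:

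1. Request `binomial(level='1' cl=wilson)`, so that the responder proportion is estimated.
2. Use `weight count / zeros`. This is needed once the level is set, because at 0/9 the responder level would otherwise be absent; with it, 0/9 gives 0–29.9%.
3. Output the Wilson limits instead of `XL_BIN`/`XU_BIN`. The programmer should confirm in SAS which output table holds them; I understand it to be `BinomialCLs`.
4. Filter on `crit1fl='Y'`, to match the code's own comment. This changes results only if the flag can be N.

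The Table 17 CI row should use the same Wilson responder limits its footnote already states. Any interim Table 16 already produced should be checked against the Wilson column above. The cost is a small edit and a test run; no data, design or analysis method changes.

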14.3 Safety Data

14.3.1 Displays of Adverse Events

Table 18: Overall Summary of Adverse Events

	Group A: 100 µg Sm-p80 (unadjuvanted) (N = X)		Group B: 10 µg Sm-p80 + 5 µg GLA-SE (N = X)		Group C: 30 µg Sm-p80 + 5 µg GLA-SE (delayed booster) (N = X)		Group D: 30 µg Sm-p80 + 5 µg GLA-SE (N = X)		Group E: 100 µg Sm-p80 + 5 µg GLA-SE (N = X)		All Subjects (N = X)	
Subjects ^a with	n	%	n	%	n	%	n	%	n	%	n	%
At least one local solicited adverse event	x	x	x	x	x	x	x	x	x	x	x	x
At least one systemic solicited adverse event	x	x	x	x	x	x	x	x	x	x	x	x
At least one unsolicited adverse event	x	x	x	x	x	x	x	x	x	x	x	x
At least one related unsolicited adverse event	x	x	x	x	x	x	x	x	x	x	x	x
Mild (Grade 1)	x	x	x	x	x	x	x	x	x	x	x	x
Moderate (Grade 2)	x	x	x	x	x	x	x	x	x	x	x	x
Severe (Grade 3)	x	x	x	x	x	x	x	x	x	x	x	x
Not yet assessed												
At least one severe (Grade 3) unsolicited adverse event	x	x	x	x	x	x	x	x	x	x	x	x
Related	x	x	x	x	x	x	x	x	x	x	x	x
Unrelated	x	x	x	x	x	x	x	x	x	x	x	x
At least one serious adverse event ^b	x	x	x	x	x	x	x	x	x	x	x	x
At least one related, serious adverse event	x	x	x	x	x	x	x	x	x	x	x	x
At least one adverse event leading to early termination ^c	x	x	x	x	x	x	x	x	x	x	x	x
At least one medically attended adverse event	x	x	x	x	x	x	x	x	x	x	x	x

Table 18: Overall Summary of Adverse Events (Continued)

	Group A: 100 µg Sm-p80 (unadjuvanted) (N = X)		Group B: 10 µg Sm-p80 + 5 µg GLA-SE (N = X)		Group C: 30 µg Sm-p80 + 5 µg GLA-SE (delayed booster) (N = X)		Group D: 30 µg Sm-p80 + 5 µg GLA-SE (N = X)		Group E: 100 µg Sm-p80 + 5 µg GLA-SE (N = X)		All Subjects (N = X)	
Subjects ^a with	n	%	n	%	n	%	n	%	n	%	n	%
At least one new onset chronic medical condition	x	x	x	x	x	x	x	x	x	x	x	x
At least one potentially immune mediated medical condition	x	x	x	x	x	x	x	x	x	x	x	x

Note: N = Number of subjects in the Safety Population
^a Subjects are counted once for each category regardless of the number of events.
^b A listing of Serious Adverse Events is included in the Serious Adverse Event Listing.
^c As reported on the Adverse Event eCRF.

Table 19: Adverse Events Occurring in 5% of Subjects in Any Treatment MedDRA System Organ Class and Preferred Term, and Treatment Group - Safety Population

Preferred Term	MedDRA System Organ Class	Group A: 100 µg Sm-p80 (unadjuvanted) (N=X)			Group B: 10 µg Sm-p80 + 5 µg GLA-SE (N=X)			Group C: 30 µg Sm-p80 + 5 µg GLA-SE (delayed booster) (N=X)			Group D: 30 µg Sm-p80 + 5 µg GLA-SE (N=X)			Group E: 100 µg Sm-p80 + 5 µg GLA-SE (N=X)			All Subjects (N=X)		
		n	%	Events	n	%	Events	n	%	Events	n	%	Events	n	%	Events	n	%	Events
Serious Adverse Events																			
All	All	x	x	x	x	x	x	x	x	x	x	x	x	x	x	x	x	x	
PT1	SOC1	x	x	x	x	x	x	x	x	x	x	x	x	x	x	x	x	x	
Etc.	Etc.																		
Other (Non-serious) Adverse Events																			
All	All	x	x	x	x	x	x	x	x	x	x	x	x	x	x	x	x	x	
PT1	SOC1	x	x	x	x	x	x	x	x	x	x	x	x	x	x	x	x	x	
Etc.	Etc.																		

Note: N = number of subjects in the Safety Population (number of subjects at risk); n = number of subjects reporting event. Events = total frequency of events reported.

14.3.1.1 Solicited Adverse Events**Table 20: Number and Percentage of Subjects Experiencing Solicited Events with 95% Confidence Intervals by Symptom and Treatment Group – Post Dose 1**

[Implementation Note: Confidence intervals will be computed via the Wilson Score method.]

Symptom	Group A: 100 µg Sm-p80 (unadjuvanted) (N=X)			Group B: 10 µg Sm-p80 + 5 µg GLA-SE (N=X)			Group C: 30 µg Sm-p80 + 5 µg GLA-SE (delayed booster) (N=X)			Group D: 30 µg Sm-p80 + 5 µg GLA-SE (delayed booster) (N=X)			Group E: 100 µg Sm-p80 + 5 µg GLA-SE (N=X)		
	n	%	95% CI ^a	n	%	95% CI ^a	n	%	95% CI ^a	n	%	95% CI ^a	n	%	95% CI ^a
Any Symptom	x	xx	x.x, x.x	x	xx	x.x, x.x	x	xx	x.x, x.x	x	xx	x.x, x.x	x	xx	x.x, x.x
Any Systemic Symptom															
[Systemic Symptom 1]															
[Systemic Symptom 2]															
Any Injection Site Symptom															
[Injection Site Symptom 1]															
[Injection Site Symptom 2]															

Note: N = Number of subjects in the Safety Population who received the specified dose; n = number of subjects reporting the specified event.

^a95% confidence intervals are from the Wilson score method without continuity correction.

Tables with similar format to [Table 20](#):

Table 21: Number and Percentage of Subjects Experiencing Solicited Events with 95% Confidence Intervals by Symptom and Treatment Group – Post Dose 2

Table 22: Number and Percentage of Subjects Experiencing Solicited Events with 95% Confidence Intervals by Symptom and Treatment Group – Post Dose 3

Table 23: Number and Percentage of Subjects Experiencing Solicited Events with 95% Confidence Intervals by Symptom and Treatment Group – Post Any Dose

Table 24: Comparison of the Proportion of Subjects Experiencing Solicited Events by Treatment Group

[Implementation Note: Confidence intervals will be computed via the Wilson Score method.]

Symptom	Statistic	Group A: 100 µg Sm-p80 (unadjuvanted) (N=X)	Group B: 10 µg Sm-p80 + 5 µg GLA-SE (N=X)	Group C: 30 µg Sm-p80 + 5 µg GLA-SE (delayed booster) (N=X)	Group D: 30 µg Sm-p80 + 5 µg GLA-SE (N=X)	Group E: 100 µg Sm-p80 + 5 µg GLA-SE (N=X)
Any Symptom	Proportion	x.xx	x.xx	x.xx	x.xx	x.xx
	95% CI ^a (for proportion)	x.xx, x.xx	x.xx, x.xx	x.xx, x.xx	x.xx, x.xx	x.xx, x.xx
	Difference		x.xx	x.xx	x.xx	x.xx
	95% CI ^a (for difference)		x.xx, x.xx	x.xx, x.xx	x.xx, x.xx	x.xx, x.xx
Any Systemic Symptom	Proportion					
	95% CI ^a (for proportion)					
	Difference					
	95% CI ^a (for difference)					
[Systemic Symptom 1]	...					
Any Injection Site Symptom	...					
[Injection Site Symptom 1]	...					

Note: N = Number of subjects in the Safety Population who received at least one dose.

^a95% confidence intervals are from the Wilson score method without continuity correction.

Table 25: Number and Percentage of Subjects Experiencing Solicited Events by Symptom, Maximum Severity, and Treatment Group – Post Dose 1

[Implementation Note: Rows for Mild, Moderate, and Severe will only be shown if there is at least one non-zero count in that row. Confidence intervals will be computed via the Wilson Score method.]

Symptom	Severity	Group A: 100 µg Sm-p80 (unadjuvanted) (N=X)			Group B: 10 µg Sm-p80 + 5 µg GLA-SE (N=X)			Group C: 30 µg Sm-p80 + 5 µg GLA-SE (delayed booster) (N=X)			Group D: 30 µg Sm-p80 + 5 µg GLA-SE (N=X)			Group E: 100 µg Sm-p80 + 5 µg GLA-SE (N=X)			All Subjects (N = X)			
		n	%	95% CI ^a	n	%	95% CI ^a	n	%	95% CI ^a	n	%	95% CI ^a	n	%	95% CI ^a	n	%	95% CI ^a	
Any Symptom	None	X	XX	X.X, X.X	X	XX	X.X, X.X	X	XX	X.X, X.X	X	XX	X.X, X.X	X	XX	X.X, X.X	X	XX	X.X, X.X	
	Mild																			
	Moderate																			
	Severe																			
Systemic Symptoms																				
Any Systemic Symptom	None	X	XX	X.X, X.X	X	XX	X.X, X.X	X	XX	X.X, X.X	X	XX	X.X, X.X	X	XX	X.X, X.X	X	XX	X.X, X.X	
	Mild																			
	Moderate																			
	Severe																			
[Systemic Symptom 1]	None																			
	Mild																			
	Moderate																			
	Severe																			
[Systemic Symptom 2]	None																			

Table 25: Number and Percentage of Subjects Experiencing Solicited Events by Symptom, Maximum Severity and Treatment Group – Post Dose 1
(Continued)

Symptom	Severity	Group A: 100 µg Sm-p80 (unadjuvanted) (N=X)			Group B: 10 µg Sm-p80 + 5 µg GLA-SE (N=X)			Group C: 30 µg Sm-p80 + 5 µg GLA-SE (delayed booster) (N=X)			Group D: 30 µg Sm-p80 + 5 µg GLA-SE (N=X)			Group E: 100 µg Sm-p80 + 5 µg GLA-SE (N=X)			All Subjects (N = X)			
		n	%	95% CI ^a	n	%	95% CI ^a	n	%	95% CI ^a	n	%	95% CI ^a	n	%	95% CI ^a	n	%	95% CI ^a	
	Mild																			
	Moderate																			
	Severe																			
Injection Site Symptoms																				
Any Injection Site Symptom	None	x	xx	x.x, x.x	x	xx	x.x, x.x	x	xx	x.x, x.x	x	xx	x.x, x.x	x	xx	x.x, x.x	x	xx	x.x, x.x	
	Mild																			
	Moderate																			
	Severe																			
[Injection Site Symptom 1]	None																			
	Mild																			
	Moderate																			
	Severe																			
[Injection Site Symptom 2]	None																			
	Mild																			
	Moderate																			
	Severe																			

Table 25: Number and Percentage of Subjects Experiencing Solicited Events by Symptom, Maximum Severity and Treatment Group – Post Dose 1
(Continued)

Symptom	Severity	Group A: 100 µg Sm-p80 (unadjuvanted) (N=X)				Group B: 10 µg Sm-p80 + 5 µg GLA-SE (N=X)				Group C: 30 µg Sm-p80 + 5 µg GLA-SE (delayed booster) (N=X)				Group D: 30 µg Sm-p80 + 5 µg GLA-SE (N=X)				Group E: 100 µg Sm-p80 + 5 µg GLA-SE (N=X)				All Subjects (N = X)			
		n	%	95% CI ^a	n	%	95% CI ^a	n	%	95% CI ^a	n	%	95% CI ^a	n	%	95% CI ^a	n	%	95% CI ^a	n	%	95% CI ^a			
Note: N = Number of subjects in the Safety Population who received the specified dose. Severity is the maximum severity reported over all solicited symptoms post dosing for each subject.																									
^a 95% confidence intervals are from the Wilson score method without continuity correction.																									

Tables with similar format to [Table 25](#):**Table 26: Number and Percentage of Subjects Experiencing Solicited Events by Symptom, Maximum Severity, and Treatment Group – Post Dose 2****Table 27: Number and Percentage of Subjects Experiencing Solicited Events by Symptom, Maximum Severity, and Treatment Group – Post Dose 3****Table 28: Number and Percentage of Subjects Experiencing Solicited Events by Symptom, Maximum Severity, and Treatment Group – Post Any Dose**

Table 29: Number and Percentage of Subjects Experiencing Solicited Events by Symptom, Severity, and Day Post Dosing – Group A: 100 µg Sm-p80 (unadjuvanted), Post Dose 1

100 µg Sm-p80 (unadjuvanted), Post Dose 1 (N=X)																			
Symptom	Severity	Pre-Dose		Post-Dose		Day 1		Day 2		Day 3		Day 4		Day 5		Day 6		Day 7+	
		n	%	n	%	n	%	n	%	n	%	n	%	n	%	n	%	n	%
Any Symptom	None	x	xx	x	xx	x	xx	x	xx	x	xx	x	xx	x	xx	x	xx	x	xx
	Mild																		
	Moderate																		
	Severe																		
	Not Reported																		
Systemic Symptoms																			
Any Systemic Symptom	None	x	xx	x	xx	x	xx	x	xx	x	xx	x	xx	x	xx	x	xx	x	xx
	Mild																		
	Moderate																		
	Severe																		
	Not Reported																		
[Systemic Symptom 1]	None																		
	Mild																		
	Moderate																		
	Severe																		
	Not Reported																		
[Systemic Symptom 2]	None																		

Table 29: Number and Percentage of Subjects Experiencing Solicited Events by Symptom, Severity, and Day Post Dosing – Group A: 100 µg Sm-p80 (unadjuvanted), Post Dose 1 (Continued)

100 µg Sm-p80 (unadjuvanted), Post Dose 1 (N=X)																			
Symptom	Severity	Pre-Dose		Post-Dose		Day 1		Day 2		Day 3		Day 4		Day 5		Day 6		Day 7+	
		n	%	n	%	n	%	n	%	n	%	n	%	n	%	n	%	n	%
	Mild																		
	Moderate																		
	Severe																		
	Not Reported																		
Injection Site Symptoms																			
Any Injection Site Symptom	None	x	xx	x	xx	x	xx	x	xx	x	xx	x	xx	x	xx	x	xx	x	
	Mild																		
	Moderate																		
	Severe																		
	Not Reported																		
[Injection Site Symptom 1]	None																		
	Mild																		
	Moderate																		
	Severe																		
	Not Reported																		
[Injection Site Symptom 2]	None																		
	Mild																		

Table 29: Number and Percentage of Subjects Experiencing Solicited Events by Symptom, Severity, and Day Post Dosing – Group A: 100 µg Sm-p80 (unadjuvanted), Post Dose 1 (Continued)

100 µg Sm-p80 (unadjuvanted), Post Dose 1 (N=X)																			
Symptom	Severity	Pre-Dose		Post-Dose		Day 1		Day 2		Day 3		Day 4		Day 5		Day 6		Day 7+	
		n	%	n	%	n	%	n	%	n	%	n	%	n	%	n	%		
	Moderate																		
	Severe																		
	Not Reported																		

Note: N = Number of subjects in the Safety Population who received the specified dose. Severity is the maximum severity reported post dosing for each subject for each day.

Tables with similar format to Table 29:

[Implementation Note: Replace header with appropriate treatment and dose.]

Table 30: Number and Percentage of Subjects Experiencing Solicited Events by Symptom, Severity, and Day Post Dosing – Group A: 100 µg Sm-p80 (unadjuvanted), Post Dose 2

Table 31: Number and Percentage of Subjects Experiencing Solicited Events by Symptom, Severity, and Day Post Dosing – Group A: 100 µg Sm-p80 (unadjuvanted), Post Dose 3

Table 32: Number and Percentage of Subjects Experiencing Solicited Events by Symptom, Severity, and Day Post Dosing – Group B: 10 µg Sm-p80 + 5 µg GLA-SE, Post Dose 1

Table 33: Number and Percentage of Subjects Experiencing Solicited Events by Symptom, Severity, and Day Post Dosing – Group B: 10 µg Sm-p80 + 5 µg GLA-SE, Post Dose 2

Table 34: Number and Percentage of Subjects Experiencing Solicited Events by Symptom, Severity, and Day Post Dosing – Group B: 10 µg Sm-p80 + 5 µg GLA-SE, Post Dose 3

Table 35: Number and Percentage of Subjects Experiencing Solicited Events by Symptom, Severity, and Day Post Dosing – Group C: 30 µg Sm-p80 + 5 µg GLA-SE (delayed booster), Post Dose 1

Table 36: Number and Percentage of Subjects Experiencing Solicited Events by Symptom, Severity, and Day Post Dosing – Group C: 30 µg Sm-p80 + 5 µg GLA-SE (delayed booster), Post Dose 2

Table 37: Number and Percentage of Subjects Experiencing Solicited Events by Symptom, Severity, and Day Post Dosing – Group C: 30 µg Sm-p80 + 5 µg GLA-SE (delayed booster), Post Dose 3

Table 38: Number and Percentage of Subjects Experiencing Solicited Events by Symptom, Severity, and Day Post Dosing – Group D: 30 µg Sm-p80 + 5 µg GLA-SE, Post Dose 1

Table 39: Number and Percentage of Subjects Experiencing Solicited Events by Symptom, Severity, and Day Post Dosing – Group D: 30 µg Sm-p80 + 5 µg GLA-SE, Post Dose 2

Table 40: Number and Percentage of Subjects Experiencing Solicited Events by Symptom, Severity, and Day Post Dosing – Group D: 30 µg Sm-p80 + 5 µg GLA-SE, Post Dose 3

Table 41: Number and Percentage of Subjects Experiencing Solicited Events by Symptom, Severity, and Day Post Dosing – Group E: 100 µg Sm-p80 + 5 µg GLA-SE, Post Dose 1

Table 42: Number and Percentage of Subjects Experiencing Solicited Events by Symptom, Severity, and Day Post Dosing – Group E: 100 µg Sm-p80 + 5 µg GLA-SE, Post Dose 2

Table 43: Number and Percentage of Subjects Experiencing Solicited Events by Symptom, Severity, and Day Post Dosing – Group E: 100 µg Sm-p80 + 5 µg GLA-SE, Post Dose 3

Table 44: Number and Percentage of Subjects Experiencing Solicited Events for Dose 1 Compared with Dose 2 and Dose 3 by Treatment Group

[Implementation Note: Add group name to treatment, e.g. "Group A: 100 µg Sm-p80 (unadjuvanted)."]

Treatment Group		Dose 2 – Subjects with No Symptoms	Dose 2 – Subjects with Moderate or Greater Symptoms	Dose 2 – Total Number of Subjects	Dose 3 – Subjects with No Symptoms	Dose 3 – Subjects with Moderate or Greater Symptoms	Dose 3 – Total Number of Subjects
Systemic Symptoms							
100 µg Sm-p80 (unadjuvanted)	Dose 1 Subject with No Symptoms	x (%)	x (%)	x (%)	x (%)	x (%)	x (%)
	Dose 1 Subjects with Moderate or Greater Symptoms	x (%)	x (%)	x (%)	x (%)	x (%)	x (%)
	Dose 1 Total Number of Subjects	x (%)	x (%)	x (100%)	x (%)	x (%)	x (100%)
10 µg Sm-p80 + 5 µg GLA-SE	Dose 1 Subject with No Symptoms						
	Dose 1 Subjects with Moderate or Greater Symptoms						
	Dose 1 Total Number of Subjects						
30 µg Sm-p80 + 5 µg GLA-SE	Dose 1 Subject with No Symptoms						
	Dose 1 Subjects with Moderate or Greater Symptoms						
	Dose 1 Total Number of Subjects						
30 µg Sm-p80 + 5 µg GLA-SE (delayed booster)	Dose 1 Subject with No Symptoms						

**Table 44: Number and Percentage of Subjects Experiencing Solicited Events for Dose 1 Compared with Dose 2 and Dose 3 by Treatment Group
(Continued)**

	Dose 1 Subjects with Moderate or Greater Symptoms						
	Dose 1 Total Number of Subjects						
100 µg Sm-p80 + 5 µg GLA-SE	Dose 1 Subject with No Symptoms						
	Dose 1 Subjects with Moderate or Greater Symptoms						
	Dose 1 Total Number of Subjects						
Local Symptoms							
100 µg Sm-p80 (unadjuvanted)	Dose 1 Subjects with No Symptoms	x (%)	x (%)	x (%)			
	Dose 1 Subjects with Moderate or Greater Symptoms	x (%)	x (%)	x (%)			
	Dose 1 Total Number of Subjects	x (%)	x (%)	x (100%)			
10 µg Sm-p80 + 5 µg GLA-SE	Dose 1 Subject with No Symptoms						
	Dose 1 Subjects with Moderate or Greater Symptoms						
	Dose 1 Total Number of Subjects						
30 µg Sm-p80 + 5 µg GLA-SE	Dose 1 Subject with No Symptoms						

**Table 44: Number and Percentage of Subjects Experiencing Solicited Events for Dose 1 Compared with Dose 2 and Dose 3 by Treatment Group
(Continued)**

	Dose 1 Subjects with Moderate or Greater Symptoms						
	Dose 1 Total Number of Subjects						
30 µg Sm-p80 + 5 µg GLA-SE (delayed booster)	Dose 1 Subject with No Symptoms						
	Dose 1 Subjects with Moderate or Greater Symptoms						
	Dose 1 Total Number of Subjects						
100 µg Sm-p80 + 5 µg GLA-SE	Dose 1 Subject with No Symptoms						
	Dose 1 Subjects with Moderate or Greater Symptoms						
	Dose 1 Total Number of Subjects						

Note: Denominators for percentages are the number of subjects in the Safety Population who received both doses being compared.

Pseudo Code:

```
/*Data Format*/
```

ID	Dose1	Dose2	Dose3
A	0	1	0
B	1	1	1
C	0	0	1
D	1	1	0

Where 0 = No Symptoms and 1 = Moderate or Greater at the given dose

```
proc freq data= t56;
tables Dose1*Dose2 / out= _dose12; /*counts for dose 1 vs. dose 2*/
tables Dose1*Dose3 / out= _dose13; /*counts for dose 1 vs. dose 3*/
run;
```

14.3.1.2 Unsolicited Adverse Events**Table 45: Summary of Unsolicited Adverse Events by MedDRA System Organ Class and Preferred Term, and Treatment Group – Post Dose 1**

MedDRA System Organ Class/ Preferred Term	Group A: 100 µg Sm-p80 (unadjuvanted) (N=X)			Group B: 10 µg Sm-p80 + 5 µg GLA-SE (N=X)			Group C: 30 µg Sm-p80 + 5 µg GLA-SE (delayed booster) (N=X)			Group D: 30 µg Sm-p80 + 5 µg GLA-SE (N=X)			Group E: 100 µg Sm-p80 + 5 µg GLA-SE (N=X)			All Subjects (N=X)		
	n	%	95% CI ^a	n	%	95% CI ^a	n	%	95% CI ^a	n	%	95% CI ^a	n	%	95% CI ^a	n	%	95% CI ^a
Any SOC	x	xx	xx, xx	x	xx	xx, xx	x	xx	xx, xx	x	xx	xx, xx	x	xx	xx, xx	x	xx	xx, xx
[SOC 1]																		
[PT 1]																		
[PT 2]																		
[SOC 2]																		
[PT 1]																		
[PT 2]																		

Note: N = number of subjects in the Safety Population who received the specified dose. This table presents number and percentage of subjects. A subject is only counted once per PT/time point.

^a95% confidence intervals are from the Wilson score method without continuity correction.

Tables with similar format to Table 45:

Table 46: Summary of Unsolicited Adverse Events by MedDRA System Organ Class and Preferred Term, and Treatment Group – Post Dose 2**Table 47: Summary of Unsolicited Adverse Events by MedDRA System Organ Class and Preferred Term, and Treatment Group – Post Dose 3**

Table 48: Unsolicited Adverse Events by MedDRA System Organ Class and Preferred Term, Maximum Severity, Relationship, and Treatment Group

MedDRA System Organ Class	Preferred Term	Severity	Group A: 100 µg Sm-p80 (unadjuvanted) (N = X)				Group B: 10 µg Sm-p80 + 5 µg GLA-SE (N = X)				Group C: 30 µg Sm-p80 + 5 µg GLA-SE (delayed booster) (N = X)				Group D: 30 µg Sm-p80 + 5 µg GLA-SE (N = X)				Group E: 100 µg Sm-p80 + 5 µg GLA-SE (N = X)				All Subjects (N = X)			
			Related		Not Related		Related		Not Related		Related		Not Related		Related		Not Related		Related		Not Related		Related		Not Related	
			n	%	n	%	n	%	n	%	n	%	n	%	n	%	n	%	n	%	n	%	n	%	n	%
Any SOC	Any PT	Any Severity	X	XX	X	XX	X	XX	X	XX	X	XX	X	XX	X	XX	X	XX	X	XX	X	XX	X	XX	X	XX
		Mild																								
		Moderate																								
		Severe																								
SOC 1	PT 1	Any Severity																								
		Mild																								
		Moderate																								
		Severe																								
	PT 2	Any Severity																								
		Mild																								
		Moderate																								
		Severe																								

Note: N = Number of subjects in the Safety Population.

Table 49: Related Unsolicited Adverse Events Within 28 Days Post Dosing by MedDRA System Organ Class and Preferred Term and Dose – Group A: 100 µg Sm-p80 (unadjuvanted) (N=X)

MedDRA System Organ Class	MedDRA Preferred Term	Post Dose 1			Post Dose 2			Post Dose 3			Post Any Dose		
		n	%	Events	n	%	Events	n	%	Events	n	%	Events
Any SOC	Any PT	x	xx	x	x	xx	x	x	xx	x	x	xx	x
[SOC 1]	Any PT												
	[PT 1]												
	[PT 2]												
[SOC 2]	Any PT												
	[PT 1]												
	[PT 2]												

Note: N = Number of subjects in the Safety Population. This table presents number and percentage of subjects. For each time point, a subject is only counted once per PT.

Tables with similar format to [Table 49](#):

Table 50: Related Unsolicited Adverse Events Within 28 Days Post Dosing by MedDRA System Organ Class and Preferred Term, and Dose – Group B: 10 µg Sm-p80 + 5 µg GLA-SE (N=X)**Table 51: Related Unsolicited Adverse Events Within 28 Days Post Dosing by MedDRA System Organ Class and Preferred Term, and Dose – Group C: 30 µg Sm-p80 + 5 µg GLA-SE (delayed booster) (N=X)****Table 52: Related Unsolicited Adverse Events Within 28 Days Post Dosing by MedDRA System Organ Class and Preferred Term, and Dose – Group D: 30 µg Sm-p80 + 5 µg GLA-SE (N=X)****Table 53: Related Unsolicited Adverse Events Within 28 Days Post Dosing by MedDRA System Organ Class and Preferred Term, and Dose – Group E: 100 µg Sm-p80 + 5 µg GLA-SE (N=X)**

